Participants will be asked to maintain their normal sleep patterns during the week prior to this visit. They will arrive in the sleep lab at 6 p.m., and the actigraph will be removed and data reviewed to confirm the participant maintained a regular sleep schedule. In addition, the sleep midpoint will be calculated from the actigraphy data to define the participant's normal 8-hour period of sleep (lights-off and lights-on) and determine the timing of all study procedures in relation to it. In other words, those with a sleep midpoint of 3 a.m. lights-out for the sleep study will be 11 p.m. and lights-on will be 7 a.m. For those with a sleep midpoint of 2 a.m., lights-out would be 10 p.m. with lights-on at 6 a.m., and for those with a sleep midpoint of 4 a.m., it would be 12 a.m. and 8 a.m. The single-item Karolinska Sleepiness Scale (KSS) and the 10-minute Psychomotor Vigilance Task (PVT) will be administered prior to sleep. The participant will then be prepared for full polysomnography with application of EEG, EOG, ECG, chin EMG, and pretibial EMG electrodes. A nasal cannula will measure nasal airflow, a thermistor will measure body temperature and a pulse oximeter will be placed on the finger to measure oxygen. Respiratory effort belts will be placed around the chest and the abdomen. Four hours after the participant's calculated sleep midpoint, the lights will be turned on and the participant awoken. The KSS and the PVT will again be administered. After this, the participant will be sent home. Individuals found to have sleep-disordered breathing (AHI>15 events/hr) on overnight polysomnography will be excluded from further testing.

Visit 5

The timing of all procedures of Visit 5 is relative to the participant's sleep midpoint. The descriptions in the Figure below are based on a hypothetical midpoint of 3 a.m. and will be adjusted accordingly to maintain the same amount of time between each procedure and the participant's actual sleep midpoint. For those participants who are eligible to complete this protocol, they will need to abstain use of caffeine, alcohol, nicotine or any illicit drugs for the entirety of their two-day visit.

Day 1

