Participants will arrive to the sleep lab by 6 p.m. The KSS is administered upon arrival and then every hour until lights-out, which will occur four hours before the participant's sleep midpoint. The PVT is administered upon arrival and then every two hours until lights-out. The Positive and Negative Affect Schedule (PANAS) is administered upon arrival and then every four hours until lights-out. Overnight polysomnography with a limited montage using only EEG, EOG, and chin EMG will be performed in order to assess sleep/wake state and sleep staging. Lights-on will be four hours after sleep midpoint. Upon awakening in the morning, participants will provide a urine sample and have a 100cc blood sample drawn. The KSS, PVT, and PANAS will again be administered every hour, every two hours, and every four hours respectively, beginning one hour after lights-on. Vascular ultrasound for brachial artery reactivity will be performed as described below. In addition to abstaining from caffeine, alcohol, nicotine, and illicit substances for the entire visit, participants will need to fast (except water) from the time of lights out through the end of vascular testing. Morning antihypertensive doses will be delayed until after vascular testing is completed. Breakfast will be served after this vascular testing. Participants will stay onsite all day, and staff will remain with them at all times (except bathroom breaks) to ensure their safety and to make sure that they stay awake with no daytime naps.

Vascular Testing

After 10 minutes of lying quietly, brachial artery diameter and flow velocities will be measured with high-resolution ultrasound equipped with an 11-L linear transducer. Image acquisition will be ECG-gated, so all measurements are done at end diastole. The brachial artery will be identified in the longitudinal plane above the antecubital fossa and a segment with clear anterior and posterior intimal interfaces between the lumen and vessel wall will be selected for continuous 2D-grayscale imaging. After obtaining baseline images, blood pressure cuff on the arm will be inflated to 50 mm Hg above resting systolic blood pressure (up to 300 mm Hg) for five minutes. After deflation, images will be obtained continuously and the maximal diameter between 30 seconds and two minutes used for calculating change. Endothelial function will be quantified as the ratio of the maximum diameter identified following cuff release to baseline diameter.

Day 2

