Participants will stay awake for the remainder of procedures. Study staff will remain with the participants at all times (except for during bathroom trips) during sleep deprivation to monitor mood and to keep them awake through conversations, playing board games, and watching television. The KSS, PVT, and PANAS will be administered every hour, every two hours, and every four hours, respectively. The participants will again be prepared with limited montage polysomnography equipment described above and will need to remain fasting (except water) starting four hours prior to sleep midpoint until vascular testing is completed (the same time frame as the prior day). In the morning, the participant will provide a urine sample and have 100cc of blood drawn at the same time as the previous day. Vascular testing will be performed as described above, after which breakfast will be served. The KSS, PVT, and PANAS will continue to be administered until seven hours after the participant's normal sleep midpoint time. At this point the participant will be provided the opportunity to have eight hours of recovery sleep, and staff will encourage them to do so for their safety before returning home. They will be allowed to leave without recovery sleep if another adult is able to drive them home.

Eligibility Criteria

Aims 1-2

Inclusion- HIV+

- 18-75 years old
- On contiguous anti-retroviral therapy (ART) regimen for at least 48 weeks
- CD4+ cell count > 200 cells/mm³

Inclusion- HIV- (Aim 1 only)

- 18-75 years old

*Note: HIV- participants are only eligible for participation in Aim 1.

Exclusion- all

- Presence of a significant sleep disorder (restless legs syndrome, narcolepsy, sleep disordered breathing on active treatment)
- Presence of an active chronic inflammatory or autoimmune disease (e.g., scleroderma, Crohn's disease)
- Regular use of medications which would impact assessment of inflammatory markers (systemic glucocorticoids, interleukins, anti-TNF drugs)
- Use of medications impacting adenosine function (theophylline or dipyridamole)
- Any initiation of an investigational/experimental therapy in the prior 30 days
- Current pregnancy

Aim 3

Inclusion

- HIV+
- Completion of Aim 1 with at least 5 days of valid actigraphy data
- On continuous anti-retroviral therapy (ART) regimen for at least 48 weeks
- CD4+ cell count > 200 cells/mm³

Exclusion

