- Atypical sleep patterns (mean sleep duration < 6 hours, sleep efficiency < 85%, standard deviation of sleep duration > 60 minutes, sleep midpoint < 2 a.m., sleep midpoint > 5 a.m.)
- Elevated risk of adverse health effects from sleep deprivation (bipolar disorder, epilepsy, history of suicidal ideation in the past 6 months)
- Heavy caffeine use (>3 caffeinated beverages per day)
- Alcohol abuse
- Drug abuse
- Daily use of medications for treatment of insomnia
- Sleep disordered breathing (AHI >15 on in-lab sleep study)
- Current pregnancy

Statistical Analysis Plan

Hypothesis 1:

The primary exposures will be four domains of sleep health: sleep duration (mean hrs/night during the main rest period), sleep fragmentation index (mean across main rest periods), sleep regularity (interdaily stability over a 14-consecutive day period), and sleep apnea severity (pAHI). Secondary measures will be mean sleep midpoint, mean diary-reported sleep quality, and

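### In habitual caffeine or nicotine users, the sleep-deprived sample comes 24 h longer after last use than the rested sample, so the Hypothesis 3 paired tests may mix sleep loss with offset or withdrawal

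*Combined protocol and SAP*

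**What the plan says.** The abstinence rule is in the Interventional Protocol, Visit 5: "they will need to abstain use of caffeine, alcohol, nicotine or any illicit drugs for the entirety of their two-day visit". Visit 5, Day 1 repeats it when introducing the fasting rule: "In addition to abstaining from caffeine, alcohol, nicotine, and illicit substances for the entire visit". Neither sentence, nor any other in the available text, sets a period before arrival.

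The timing comes from the same section:

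- Arrival: "Participants will arrive to the sleep lab by 6 p.m".
- Waking: "Lights-on will be four hours after sleep midpoint".
- Rested sample: "Upon awakening in the morning, participants will provide a urine sample and have a 100cc blood sample drawn".
- Sleep-deprived sample, after the night awake: participants "have 100cc of blood drawn at the same time as the previous day".

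On entry, the Aim 3 exclusions remove people who drink more than three caffeinated beverages a day, and those with alcohol or drug abuse. Nicotine use is not on the list. Visit 3 asks about both caffeine and nicotine use.

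The Statistical Analysis Plan tests Hypothesis 3 with paired t-tests, or signed-rank tests where needed, of baseline against post-deprivation values. Its secondary analyses consider sex, CD4+ count and viral load as modifiers of the response. Caffeine and nicotine appear nowhere in the Hypothesis 3 analysis. Habitual caffeine use does appear as a possible confounder for Hypothesis 2.

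**The concern.** Every participant goes through the same sequence, rested first and deprived second, under one continuous spell of abstinence. Two things therefore change together between the samples: a night of sleep is lost, and a further day passes without caffeine or nicotine. In a non-user the second change is empty. In a user it is not, and nothing in the design separates it from the first. There is no counterbalancing and no second rested night under the same abstinence.

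Both possible directions matter. Hypothesis 3 predicts the absence of a compensatory rise in adenosine, and the presence of a rise in inflammation with worse endothelial function. An extra shift in users could create or hide either pattern. Elsewhere the protocol takes care to match the two mornings: clock time of the draw, fasting window and vascular procedure are all aligned. Time since last caffeine or nicotine is a short-term influence that is not aligned.

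**Working it through.** The documents give no abstinence interval, so there is no figure of the plan's own to reproduce. The check is clock arithmetic.

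**Inputs.** Latest permitted use: 6 p.m. arrival (Visit 5, Day 1). Waking: midpoint plus 4 h (Visit 5, Day 1). Second draw: same clock time the next day (Visit 5, Day 2). Permitted midpoints: 2 a.m. to 5 a.m. (Aim 3 exclusions). Reference case: "The descriptions in the Figure below are based on a hypothetical midpoint of 3 a.m".

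**Formulas.** Hours from arrival to the rested draw = 6 (6 p.m. to midnight) + midpoint + 4. Hours to the deprived draw = that + 24.

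| Midpoint | Lights-on | Rested draw | Deprived draw | Gap | Ratio |
|---|---|---|---|---|---|
| 2 a.m. | 6 a.m. | 6+2+4 = 12 h | 36 h | 24 h | 3.0 |
| 3 a.m. | 7 a.m. | 6+3+4 = 13 h | 37 h | 24 h | 2.85 |
| 4 a.m. | 8 a.m. | 6+4+4 = 14 h | 38 h | 24 h | 2.71 |
| 5 a.m. | 9 a.m. | 6+5+4 = 15 h | 39 h | 24 h | 2.6 |

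These are minimum intervals. Earlier last use lengthens both and leaves the gap at 24 h. They apply to blood and urine. The vascular test has no stated clock time, but it follows the same procedure on both mornings.

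**What the paired test estimates.** Let δ be the mean change due to sleep loss, ω the mean extra change in users due to the additional 24 h without caffeine or nicotine, and p the proportion of users. Take δ to be the same in users and non-users. The expected paired mean change is then

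δ(1 − p) + (δ + ω)p = δ + pω.

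The bias pω runs from 0 (no users, or no offset or withdrawal effect) to ω (all users). It does not shrink as the sample grows. The documents give neither p nor ω.

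**Illustration for residual caffeine only.** The half-life is not in the documents, so I assume 3, 5 or 7 h. Residual fraction = 0.5^(hours / half-life).

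| Last use, 3 a.m. midpoint | Hours to rested draw | 3 h | 5 h | 7 h |
|---|---|---|---|---|
| 6 p.m. (latest permitted) | 13 | 5% | 17% | 28% |
| Noon | 19 | 1% | 7% | 15% |

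At the deprived draw after 6 p.m. use (37 h), the fractions are 0.02%, 0.6% and 2.6%. So under these assumptions residual exposure at the rested draw may be trivial or appreciable, depending on habits that the documents do not describe. This says nothing about nicotine, about withdrawal, or about the effect on any outcome.

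**Would earlier abstinence close the gap?** Starting 24 h before arrival gives 13 + 24 = 37 h and 37 + 24 = 61 h. The difference is still 24 h; the ratio falls from 2.85 to 1.65.

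**The case against.** The strongest reply is that elapsed time is not bias. Any rested-then-deprived sequence under continuous abstinence has a 24 h gap, and nothing in the documents shows that one more day without caffeine or nicotine moves soluble CD14, soluble CD163 or IL-6, the primary outcomes. That stands. The claim can be only that the comparison may be confounded in users.

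Three further points are also sound:

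- A reader might infer that the rested sample falls outside the abstinent period. It does not; both draws lie within it.
- A reader might infer that leaving habitual caffeine out of Hypothesis 3 contradicts its use in Hypothesis 2. It does not. Hypothesis 2 compares different people, whereas in a within-person contrast stable differences in habit cancel. Only an effect that changes between the two mornings remains.
- The absence of a pre-visit rule is inferred from silence. The Visit 5 figure is not shown, and consent pages were removed from the text; either could carry an instruction.

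The exclusion of heavy caffeine users and continuous staff presence are partial controls. They reduce the caffeine problem but do not remove it, and the entry criteria do nothing for nicotine. None of these points gives the planned paired test a way to tell the two explanations apart in users.

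**Conclusion.** The concern holds as a limit on attribution. In users, time since last caffeine or nicotine is 24 h longer at the deprived draw than at the rested draw, with at least 13 and 37 h for a 3 a.m. midpoint. The fixed order and the lack of a rested second-night control mean that the planned tests cannot separate this from sleep loss.

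The conclusion assumes that participants comply with abstinence, that some enrolled participants use caffeine or nicotine, and that no pre-visit rule exists in the parts not shown. If a pre-visit rule exists, residual exposure at the rested draw is lower, but the 24 h difference remains.

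A reader might go further and infer that Hypothesis 3 is invalid, or that a known part of the change is withdrawal. The documents do not support that: they give neither the number of users nor any effect on the outcomes, so the bias could be nil and its sign is unknown. Nor do they support the idea that an earlier start of abstinence would cure the problem, as the arithmetic above shows.

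**What to change.** Add to the Hypothesis 3 section of the Statistical Analysis Plan, before outcome data are examined (if they have been examined already, label the analyses post hoc):

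1. **Sensitivity analysis.** Report the paired change, with its confidence interval, in participants who use neither caffeine nor nicotine, beside the change in users.
2. **Regression of the change.** Regress each participant's change on habitual caffeine and nicotine use recorded at Visit 3. Code both as zero for no use, without centring, so that the intercept estimates the change at zero use.
3. **Interpretation rule.** If the effect is absent or clearly smaller in non-users, do not attribute the overall change to sleep loss alone. Judge this on estimates and intervals, not on whether one subgroup reaches significance.

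The cost is a small amount of analysis on information that Visit 3 already asks for. The downside is precision. The documents state no sample size, the non-user group may be small, and with few non-users the intercept becomes an extrapolation. Users and non-users may also differ in other ways, so a difference between them would be a warning and not proof of withdrawal. The documents do not say how much detail on use is recorded; if it is only yes or no, item 2 becomes a comparison of groups.

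Optionally, if visits remain, the sponsor may consider starting abstinence before arrival. That would lower residual exposure at the rested draw, at the price of a longer restriction on participants, but it would not remove the 24 h difference and does not replace the analyses above.

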Given the high prevalence of poor sleep among PLWH and the growing understanding of the adverse consequences of poor sleep, obtaining a better biological understanding of how poor sleep may interact with HIV infection not only will provide the rationale to develop public health interventions to improve sleep in this high-risk population, but also will inform the identification of novel interventions that might minimize the adverse effects of poor sleep and improve non-infectious outcomes in PLWH. Drugs that modulate adenosine signaling (such as dipyridamole which increases extracellular adenosine levels) are already clinically available and could be readily utilized to improve outcomes if our hypotheses are proven accurate.

This proposal is highly innovative in being the first to test the impact of poor sleep on adenosine signaling in lymphocytes and monocytes, a pathway already established to be impaired in the setting of HIV infection and hypothesized to contribute to the persistent inflammation and long-term cardiopulmonary morbidity observed in PLWH. Further, this proposal will be the first to directly test the hypothesis that poor sleep and HIV infection have a synergistic impact on inflammation through the adenosine pathway.

From a methodologic standpoint, this will be one of the first large-scale assessments of sleep in an HIV+ population to use objective assessments of sleep. In addition, we will use a multi-dimensional framework to comprehensively assess sleep. Finally, we will separately assess both long-term effects of chronically poor sleep as well as short-term effects of acute and sub-acute

sleep loss, providing a comprehensive understanding of the interaction between sleep, inflammation, and adenosine signaling that can lead to the development of intervention strategies to decrease the levels of inflammation and subsequently the risk for cardiopulmonary comorbidities in PLWH.

Study Objectives

In this proposal we seek to test the hypothesis that one mechanism by which poor sleep may impact inflammation and cardiopulmonary risk in people living with HIV is via effects on peripheral adenosine signaling. We will do this by performing a cross-sectional evaluation to test Hypotheses 1-2 and an interventional study to perform a within-subject analysis to test Hypothesis 3.

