Hypothesis 1: Objectively measured poor sleep is associated with greater levels of inflammation and markers of cardiopulmonary disease among antiretroviral therapy (ART)-treated people living with HIV (PLWH) compared to those without HIV.

Hypothesis 2: Among ART-treated PLWH, downregulation of the adenosine pathway is associated with objectively measured markers of poor sleep.

Hypothesis 3: Acute sleep deprivation in ART-treated PLWH does not produce a compensatory increase in extracellular adenosine generation and signaling, leading to increased inflammation and endothelial dysfunction.

Study Design & Methods

Research Activities:

Recruitment

Individuals with and without HIV will be recruited through advertising in local longitudinal research cohorts studying PLWH, by advertising through clinics that care for PLWH and patients at high risk for developing HIV, and through platforms developed for recruiting people in the community interested in participating in research. Telephone screening will be performed to assess eligibility and review the study protocol. Individuals who meet eligibility criteria and are interested in participating will be scheduled for an in-person study visit.

Cross-Sectional Protocol

Visit 1

A point-of-care urine pregnancy test will be given to women of child-bearing potential. If the pregnancy test is positive, the participant will be ineligible for the study and procedures will be discontinued. The participant will then be asked to complete a battery of interviewer-administered questionnaires. This battery consists of questions on demographics, education, work schedule, caffeine use, nicotine use, and the reduced Morningness Eveningness Questionnaire (rMEQ) to assess circadian preference. Participants will have a wrist actigraph (Respironics Spectrum) placed on the non-dominant wrist and instructed to wear for two weeks. They will be given instructions

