We will compare the frequencies of immune cells expressing ectonucleotidases (CD39+ T cells, CD73+ T cells, and CD39+ CD73+ T cells), monocyte adenosine receptor expression (A1R and A2AR), ADO and inosine levels, and measures of T cell activation between those HIV+ subjects with healthy and poor sleep. Ectonucleotidase expression on B cells and monocytes, additional purine pathway metabolites, and frequencies of CD14+ monocytes expressing IL-6 and/or TNF α will also be compared in secondary analyses. Analyses will initially use t-tests for normally distributed variables or Mann Whitney tests for non-normal distributions. Subsequent analyses will consider potential confounders (age, sex, CD4+ T cell count, viral load, habitual caffeine use, chronotype, sleep midpoint) and adjust in multivariable linear regression for the set of variables that differ between the healthy and poor sleep groups at $p < 0.10$. Sex-related differences will be tested by evaluating the statistical significance of a sex * sleep interaction term.

Hypothesis 3:

The primary outcome measures are levels of soluble CD14, soluble CD163, and circulating IL-6 levels. Secondary outcome measures are flow mediated dilation (percent change in brachial artery diameter to reactive hyperemia), monocyte expression of IL-6, monocyte expression of TNF α , frequency of CD4+ T cells expressing HLA-DR and CD38, and frequency of CD8+ T cells expressing HLA-DR and CD38. Additional pre-specified outcomes include plasma adenosine and inosine levels, urinary 3'5'-cAMP, and frequencies of CD4+ and CD8+ T cells expressing CD39

and CD73. The impact of sleep deprivation will be assessed by performing paired t-tests of each of these outcomes comparing baseline to post-sleep deprivation values. For variables with non-normal distributions, we will either transform variables or use Wilcoxon signed-rank tests. The correlation between the changes in each domain (expressed as percent change from baseline) will be calculated to assess the extent to which change in endothelial function may be predicted by change in inflammation or ADO signaling and change in inflammation by change in ADO signaling. Secondary analyses will consider the extent to which sex, CD4+ T cell count, and viral load impact sensitivity to sleep deprivation by regressing each of these potential effect modifiers on the percent change in each of the primary outcome measures for inflammation, endothelial function, and ADO signaling.

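### Aim 3 matches the two blood draws on clock time and fasting but not on posture, so a plasma-volume shift in the predicted direction cannot be excluded from the primary comparison

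*Combined protocol and SAP*

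**What the plan says.** The Study Objectives describe "an interventional study to perform a within-subject analysis to test Hypothesis 3". Hypothesis 3 predicts that acute sleep deprivation fails to raise adenosine signalling, "leading to increased inflammation and endothelial dysfunction".

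Under Visit 5, Day 1, the rested night begins at "lights-out, which will occur four hours before the participant's sleep midpoint" and ends as follows: "Lights-on will be four hours after sleep midpoint". The baseline sample comes next: "Upon awakening in the morning, participants will provide a urine sample and have a 100cc blood sample drawn". Urine is listed before blood. No number of minutes and no posture is given.

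Under Visit 5, Day 2, staff stay with participants to "keep them awake through conversations, playing board games, and watching television". In the morning participants give urine and "have 100cc of blood drawn at the same time as the previous day". Again no posture is given.

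The Visit 5 text matches the fasting window (water allowed), the limited polysomnography set-up, and abstinence from caffeine, alcohol, nicotine and illicit drugs. The Vascular Testing section requires 10 minutes of quiet lying before the ultrasound. There is no counterpart for phlebotomy.

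The Statistical Analysis Plan, Hypothesis 3, states: "The primary outcome measures are levels of soluble CD14, soluble CD163, and circulating IL-6 levels". Each outcome is compared between baseline and post-deprivation by a paired t-test, with transformation or a signed-rank test if it is not normal. No plasma-volume adjustment is described.

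**The concern.** Moving from lying to sitting or standing shifts fluid out of the circulation. Proteins that stay in the circulation then become more concentrated without any change in their production. If participants come to the rested draw shortly after 8 hours in bed, and to the deprived draw after hours mostly out of bed, the second sample would tend to be the more concentrated one.

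Nothing in the design would reveal this. The order is fixed (rested, then deprived), there is no undeprived control night, and the test compares raw or transformed concentrations. Any systematic difference in draw conditions goes into the paired difference. Here it would have the sign that Hypothesis 3 predicts for sCD14, sCD163 and IL-6, so a modest rise could be reported as inflammation from sleep loss when part or all of it was fluid shift. Unlike wakefulness, posture just before a draw is not part of the intervention and can be matched.

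The point is limited to concentrations. Cell frequencies and the brachial diameter ratio are not inflated this way. For plasma adenosine and inosine the artefact would work against the hypothesis of no compensatory increase.

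**Working it through.** **What the text fixes for each draw**

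| | Rested draw (Day 1) | Deprived draw (Day 2) |
|---|---|---|
| Preceding 8 h | lights out, midpoint − 4 h to midpoint + 4 h | awake |
| Clock time | on awakening | same as Day 1 |
| Fasting | from lights-out | same window |
| Posture or rest before draw | not stated | not stated |

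**Size.** The documents give no sample size, SD, effect size or posture figure for Aim 3, so there is no stated figure to reproduce. All inputs below are assumptions:

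- x, plasma volume lower at the deprived draw: 3%, 5%, 10%
- marker fully retained in plasma
- SD of the within-person change in log concentration: 0.15 (stable marker) or 0.40 (noisy marker)
- n = 20 or 30
- two-sided 5% test (no level is stated for Hypothesis 3; the only stated one is for the HIV interaction under Hypothesis 1)
- no true effect of sleep loss

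**Formulas.** Concentration ratio = 1/(1 − x). Shift on the log scale d = −ln(1 − x). Noncentrality = d√n / SD. False rejection = probability that a noncentral t with n − 1 degrees of freedom falls outside the critical values.

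**Worked case.** x = 5%, n = 30, SD 0.15: ratio 1/0.95 = 1.053; d = 0.0513; noncentrality = 0.0513 × 5.477 / 0.15 = 1.87; critical value 2.045 on 29 df; rejection 44%.

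| x | Rise in concentration | n = 30, SD 0.15 | n = 30, SD 0.40 | n = 20, SD 0.15 |
|---|---|---|---|---|
| 3% | 3.1% | 19% | 7% | 14% |
| 5% | 5.3% | 44% | 10% | 31% |
| 10% | 11.1% | 96% | 29% | 85% |

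**After matching.** With x = 0 the rate returns to 5%. With a residual x of 1%, n = 30 and SD 0.15, it is 6.5%.

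**Which correction is safe.** Day 1 removes 100cc of blood. With an assumed blood volume of 4 to 6 L and no replacement within a day, that is 100/6000 = 1.7% to 100/4000 = 2.5% of red cells. A haematocrit-only formula assumes constant red-cell mass, so it would read this loss as plasma expansion. It would multiply corrected Day 2 concentrations by 1/(1 − 0.017) to 1/(1 − 0.025), a spurious rise of about 1.7% to 2.6%, also in the predicted direction.

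**The case against.** The strongest reply is that the posture contrast is inferred. The Day 2 text says participants stay awake; it does not say they are upright, and conversation, board games and television can all be done seated or reclined. On Day 1 urine is listed before blood, so some time out of bed before the rested draw is likely. The first sleepiness and vigilance tests come one hour after lights-on, so the text does not limit that time to a few minutes. The Visit 5 schedule figure is not in the text available here and may state draw times or conditions. A further volume effect could run the other way: fluid refill after the 100cc Day 1 draw would dilute the Day 2 sample. Finally, the size depends wholly on assumed inputs.

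All of this stands as a limit on how strongly the point can be put. A reader might infer that participants are kept upright all night, that the rested blood is taken lying down or nearly so, or that the paired difference carries the whole posture effect. The documents state none of these.

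The reply does not remove the point. The written schedule puts one draw at the end of 8 hours in bed and the other at the end of a night awake, which makes some difference in recent posture probable. It leaves that difference to chance and does not record it. An opposing dilution effect of unknown size does not guarantee cancellation, and is itself a reason to measure plasma dilution. The ultrasound rule shows that a pre-measurement rest is feasible in this setting.

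**Conclusion.** The concern holds in a limited form. As written, the plan neither matches nor records posture before the two Aim 3 draws and plans no plasma-volume adjustment. A posture artefact in the predicted direction therefore cannot be excluded from any of the three primary comparisons.

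Whether it matters depends on the marker. With n = 30 and a 3% to 5% plasma-volume difference, false rejection is 19% to 44% at SD 0.15 but 7% to 10% at SD 0.40. These figures assume full retention of the marker, no true effect and a two-sided 5% level, and none of their inputs comes from the documents. The 96% entry needs a 10% difference, low variability and n = 30 together, and should not be read as the expected rate.

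A reader might go further and conclude that a rise in sCD14 or sCD163 in this study would be haemoconcentration. The documents do not support that, because they give neither the posture at either draw nor the size of any shift. What can be said is that the two explanations could not be told apart. The change is worth making because it is cheap and alters what is done at the bedside, not merely how it is described.

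**What to change.** In Visit 5, Day 1 and Day 2, state that blood is drawn at the same fixed interval after the lights-on time (on Day 2, the matching clock time), after the same fixed period in the same posture. For example, 30 minutes seated and awake on both mornings. Record posture and draw time. If the schedule figure already sets such conditions, carry them into the text.

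Measure total protein or albumin in both samples, and add to the Hypothesis 3 analysis a sensitivity analysis of sCD14, sCD163 and IL-6 adjusted for the change in that protein. Do not rely on haematocrit alone, for the reason shown in the working. The adjustment assumes that the marker and the reference protein concentrate to a similar degree, so it supports the matched draw and does not replace it.

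The cost is a sentence or two of protocol text and a routine assay on blood already drawn. The downside is that the Day 1 draw, and the procedures after it, move about 30 minutes later on both days. A draw at 30 minutes still precedes the first sleepiness and vigilance tests, which start one hour after lights-on. The fast runs to the end of vascular testing, so it lengthens if that testing moves.

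If the draws are already complete, report unmatched posture as a limitation and, if stored plasma permits, measure total protein or albumin in it.
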